### **10.3.5. Pharmacodynamic Analyses**

All participants in the ITT population will be included in the summaries of PD data. The actual value, change from baseline and percentage change from baseline for all PD parameters will be summarized by visit and treatment group using the n, mean, SD, median, first and third quartiles, minimum, and maximum values. Statistical testing may be performed between the two treatment groups using mixed models. Details will be provided in the Statistical Analysis Plan.

Serum IgG, IgG subclass (1-4), and anti-AChR levels will be summarized as both raw values as well as percent change from baseline (intra-participant assessment). Additional PK/PD and PD/PD relationships may be evaluated. PD data will be presented in graphical and tabular form and will be summarized descriptively.

The comparison of the active arms (separately) to the placebo arm will be performed using an Analysis of Covariance model with treatment and baseline value in the model. An alpha of 0.05 will be used to determine statistical significance.

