3. TYPE OF PLANNED ANALYSIS AND ALPHA ALLOCATION

Per protocol, an interim analysis will occur after the last subject completes the Week 7 visit of the study. All efficacy endpoints will be evaluated for this analysis. It is noted that the planned interim/primary analysis is the final analysis of the complete dataset from the double-blind treatment period. The database is interim due to the follow-up period, in which safety data will continue to accrue and be updated.

Due to COVID-19 impact on the study, an interim analysis may be done after 15 subjects have completed Week 7, although the study is continuing. An interim analysis plan (IAP) will guide any interim analysis that is done. The IAP will document disclosure and safeguards to protect the integrity of the ongoing study.

A final analysis will occur when the last subject completes or discontinues the study and the database is locked.

An additional analysis of the anti-RVT-1401 antibody data will be performed if any subjects require follow-up testing. This analysis will focus solely on the antibody data and does not require any alpha correction. The CSR will be amended with this additional analysis if it is necessary.

Alpha is controlled through the conditional sequencing of hypotheses. No other adjustment for multiplicity is needed. The interim analysis, if done, will be executed for administrative purposes due to business needs in response to circumstances precipitated by COVID-19 issues. Alpha is allocated for the interim analysis of 0.0001, which is considered to be negligible; consequently, the final analysis has alpha = 0.05 preserved.

4. **BLINDING**

At the time of the finalization of this SAP, no unblinding of any kind has occurred. It is noted that the only unblinded personnel for the study are documented in planning documents. Immunovant supports strong process and has standard operating procedures (SOPs) consistent with written regulatory guidance and standard conventions to protect the blinding of this study.

Selected laboratory analytes that may reveal the treatment for individual subjects are conveyed and stored in protected spaces with controlled access to safeguard further the treatment given to specific subjects.

There are four sources of unblinding or potential unblinding for this study:

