5.4. Multiple Comparisons

Adjustments for multiple comparisons for the primary efficacy endpoints list in Section 9.2 will be performed using a fixed, sequential testing procedure. The order of the testing sequence is specified in Section 9.2. The first test in the sequence will be performed at a significance level of 0.05. If that test is significant, then the second test in the sequence will be performed at a significance level of 0.05, and so on. Testing will stop when a non-significant test occurs in order to maintain a family-wise error rate of alpha=0.05.

There will be no adjustments for multiple comparisons for the secondary efficacy or OLE endpoints.

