9.2. Statistical Hypotheses for the Efficacy Endpoints

The efficacy endpoint hypotheses will be tested in the order below.

1. $H_0: \mu_{11} = \mu_{1p}$ vs. $H_A: \mu_{11} \neq \mu_{1p}$, where μ_{11} = LSmean of $\% \Delta_{\text{Total IgG}}$ for RVT-1401 680 mg/wk or RVT 340 mg/wk and μ_{1p} = LSmean of $\% \Delta_{\text{Total IgG}}$ for placebo

Supportive superiority on percent change in IgG is evaluated:

- H_{01} : The percent change from baseline in Total IgG after 6 weeks of treatment for the group treated with RVT-1401 680 mg/wk is equal to that of the placebo group.
- H_{11} : The percent change from baseline in IgG after 6 weeks of treatment for the group treated with RVT-1401 680 mg/wk is not equal to that of the placebo group.

Supportive superiority on percent change in IgG is evaluated:

- H_{02} : The percent change from baseline in IgG after 6 weeks of treatment for the group treated with RVT-1401 340 mg/wk is equal to that of the placebo group.
- H_{12} : The percent change from baseline in IgG after 6 weeks of treatment for the group treated with RVT-1401 340 mg/wk is not equal to that of the placebo group.

Superiority on percent change in anti-AChR-IgG level is evaluated:

- H_{03} : The percent change from baseline in *anti-AChR-IgG* after 6 weeks of treatment for the group treated with RVT-1401 680 mg/wk is equal to that of the placebo group.
- H_{13} : The percent change from baseline in *anti-AChR-IgG* after 6 weeks of treatment for the group treated with RVT-1401 680 mg/wk is not equal to that of the placebo group.

evaluation continues:

- H_{04} : The percent change from baseline in *anti-AChR-IgG* after 6 weeks of treatment for the group treated with RVT-1401 340 mg/wk is equal to that of the placebo group.
- H_{14} : The percent change from baseline in *anti-AChR-IgG* after 6 weeks of treatment for the group treated with RVT-1401 340 mg/wk is not equal to that of the placebo group.

Conditional on the p-value being less than alpha, testing continues:

Superiority on change in MG-ADL is evaluated:

- H_{05} : The percent change from baseline in *MG-ADL* after 6 weeks of treatment for the group treated with RVT-1401 680 mg/wk or RVT 340 mg//wk is equal to that of the placebo group.
- H_{15} : The percent change from baseline in *MG-ADL* after 6 weeks of treatment for the group treated with RVT-1401 680 mg/wk or RVT-1401 340 mg/wk is not equal to that of the placebo group.

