12. PHARMACODYNAMIC ANALYSES

Pharmacodynamic endpoints (total IgG, IgG1, IgG2, IgG3, IgG4, and anti-AChR-IgG level) will be summarized descriptively and analyzed using an ANCOVA model. Descriptive statistics (sample size, mean, standard deviation, median, Q1, Q3, minimum and maximum) of baseline, post-baseline, change from baseline, and percentage change from baseline values for each PD endpoint will be provided by treatment group for all scheduled visits.

The ANCOVA model with treatment as a fixed factor, and baseline value as covariate will be used to produce least-squares means and 95% CIs for each treatment group at each scheduled visit. For each scheduled visit, the least-squares means will be compared using a t-test. Line plots of the least squares means and 95% CIs by visit will also be provided.

There will be no adjustments for multiple comparisons of PD endpoints. An alpha level of 0.05 will determine statistical significance. Analyses of PD endpoints will be provided for the PD analysis population.

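### SAP 12 applies an unadjusted 0.05 at every visit to total IgG and anti-AChR-IgG, although their Week 7 by-dose comparisons sit in the fixed sequence of SAP 5.4 and 9.2; the practical exposure is anti-AChR-IgG

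*SAP*

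**What the plan says.** **The sequence.** SAP 5.4 states that adjustment for the primary efficacy endpoints listed in 9.2 "will be performed using a fixed, sequential testing procedure", and that "Testing will stop when a non-significant test occurs in order to maintain a family-wise error rate of alpha=0.05". SAP 9.2 opens with "The efficacy endpoint hypotheses will be tested in the order below". It then lists total IgG for 680 or 340 mg, total IgG by dose (H01 for 680 mg, H02 for 340 mg), anti-AChR-IgG by dose (H03 for 680 mg, H04 for 340 mg), and two MG-ADL hypotheses (H05, H06). SAP 3 makes this the only control: "Alpha is controlled through the conditional sequencing of hypotheses. No other adjustment for multiplicity is needed".

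**The exemptions.** SAP 5.4 names the endpoints that go unadjusted: "There will be no adjustments for multiple comparisons for the secondary efficacy or OLE endpoints". Pharmacodynamic (PD) endpoints are not among them.

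**The other rule.** SAP 12 says: "Pharmacodynamic endpoints (total IgG, IgG1, IgG2, IgG3, IgG4, and anti-AChR-IgG level) will be summarized descriptively and analyzed using an ANCOVA model". The model has treatment and baseline, the least-squares means are compared at each scheduled visit, and the PD analysis set is used. The section closes its multiplicity policy with "There will be no adjustments for multiple comparisons of PD endpoints. An alpha level of 0.05 will determine statistical significance".

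**The protocol.** Protocol 10.3.5 says: "The comparison of the active arms (separately) to the placebo arm will be performed using an Analysis of Covariance model". It also sets alpha at 0.05 for these comparisons and mentions no sequence. Protocol Section 4 lists change in total IgG, in the four IgG subclasses and in anti-AChR-IgG among the primary endpoints.

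**The concern.** Week 7 is a scheduled visit, so SAP 12 covers the comparisons that 9.2 numbers H01 to H04. It does not refer to 5.4 or 9.2 and does not call its p-values nominal. It says that 0.05 decides significance.

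Suppose H01 and H02 succeed, H03 gives p=0.08 and H04 gives p=0.03. Under SAP 5.4 the sequence stops at H03, and the 340 mg effect on anti-AChR-IgG cannot be claimed. Under SAP 12 it is significant. Anti-AChR-IgG is part of a primary objective and of the primary variable in SAP 8.3, so this choice would be visible in the study report. It should not be open once the data are seen.

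**Working it through.** **1. The plan's own figure.** In a fixed sequence a false claim requires rejecting the first true null hypothesis, which is tested at 0.05, so the family-wise error rate is at most 0.05. A simulation (200,000 trials, 7 per arm, shared placebo arm, two-sided pooled-variance t-tests on 18 degrees of freedom) gave 0.0497 to 0.0505. The first test was taken as the two active arms combined against placebo. The stated 0.05 is reproduced.

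**2. Which tests can split.** The first test in 9.2 is at 0.05 with nothing ahead of it, so the two alpha rules agree on it. Only H01 to H04 can differ.

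**3. Is total IgG likely to be borderline?** Inputs: expected reductions of 75-80% (680 mg) and 65-70% (340 mg) from Protocol 3.2.2; SD 20 from SAP 1.3; 7 per arm.
- Standard error of a difference = 20 × √(2/7) = 10.69.
- 340 mg: 65/10.69 = 6.08, and 6.08 − 1.96 = 4.12, so power exceeds 99.9%.
- 680 mg: 75/10.69 = 7.02, and 7.02 − 1.96 = 5.06, so power is higher still.

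In the simulation the sequence passed all the total IgG steps in 99.99% of trials.

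**4. Total IgG truly reduced (75 and 65 points), anti-AChR-IgG null.** SD 20 was assumed for both analytes, with a between-analyte correlation of 0 to 0.8.

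| Rule | False-positive rate, anti-AChR-IgG |
|---|---|
| Sequence (5.4/9.2) | 0.050 |
| Unadjusted 0.05 (SAP 12) | 0.088 to 0.090 |

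Two independent tests would give 1 − 0.95² = 0.0975; the shared placebo arm lowers this slightly. The rules disagree when H03 fails and H04 has p<0.05, that is, in about 0.09 − 0.05 = 0.04 of trials (simulated 0.039 to 0.040).

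**5. Global null.** Four independent tests would give 1 − 0.95⁴ = 0.1855. With the shared placebo arm and correlation 0 to 0.8, the simulated rate is 0.170 down to 0.139. The rules then disagree on at least one of H01 to H04 in 12% to 14% of trials.

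**6. Anti-AChR-IgG truly reduced.** Assumed reductions were 20 to 50 points, with correlation 0.5. With SD 20 the rules disagree in 0.6% (50 points at both doses) to 15% (20 points at both doses) of trials. With SD 30 the range is 7% to 17%, but there total IgG was also given SD 30, so a few of those disagreements may arise at H02. These are differences in what may be claimed, not false positives.

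The simulations leave out the baseline covariate and missing data.

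**The case against.** **The gate on H01 to H04 is inferred.** The explicit condition that testing continues only after a significant p-value stands in 9.2 only before H05 and H06. The by-dose total IgG tests are introduced as supportive. This stands as an ambiguity. The gate rests on 5.4, which covers the endpoints listed in 9.2, and on the ordering sentence that opens 9.2. It is the better reading, and the plan should state it.

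**SAP 12 reads naturally as a supportive by-visit section.** SAP 9.3 contains the primary hypothesis test, on the full analysis set (FAS) and with multiple imputation if two or more subjects lack Week 7 data. SAP 12 uses the PD set, gives no imputation rule of its own, and does not say whether the modelled response is the value, the change or the percentage change. It therefore cannot be called the identical analysis. But its text does not say supportive; it says that 0.05 determines significance. The differences add a second way for one hypothesis to receive two answers.

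**Stronger readings to avoid.** A reader might infer that the primary endpoint can fail under one section and succeed under the other. SAP 9.1 names total IgG at Week 7 as the primary efficacy endpoint, and the alpha rule cannot split its first test. A reader might also infer that family-wise control is lost altogether, but the 9.2 sequence does hold 5%. Nor should an error rate over all six analytes be set against that 5%: the four subclasses are not in the sequence, and 5% was never claimed for them.

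**The consequence is limited.** This is a Phase 2a trial of about 21 participants, meant to support a larger confirmatory study. That lowers the stakes but does not remove the contradiction.

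**Conclusion.** The SAP gives two significance rules for H01 to H04 at Week 7, and no other section reconciles them; SAP 14 does not mention the matter. In practice the exposure is anti-AChR-IgG by dose. Where total IgG responds as the protocol expects and anti-AChR-IgG does not, using SAP 12 raises the anti-AChR-IgG false-positive rate from 5% to about 9%. The 14% to 17% for all four tests applies only if total IgG is null too, which the protocol's Phase 1 data make unlikely.

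The sizes rest on 7 per arm, SD 20 and assumed correlations; the documents give no correlation, and no effect or SD for anti-AChR-IgG. The textual conflict depends on none of these. It is a clarification worth making before unblinding. The status of anti-AChR-IgG also needs one definition, since SAP 9.1 calls it supportive and SAP 8.3 places it in the primary endpoint.

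**What to change.** 1. In SAP 12, state that significance for the Week 7 total IgG and anti-AChR-IgG comparisons is decided only by the SAP 5.4/9.2 sequence, applied to the SAP 9.3 analysis (FAS, percentage change from baseline).
2. Remove the 0.05 decision rule from the rest of SAP 12. Label the p-values for the four subclasses, and for all visits other than Week 7, as nominal, and show them with 95% confidence intervals.
3. Record this in SAP 14 as a change from Protocol 10.3.5, which sets 0.05 for these comparisons, and from Protocol Section 4, which lists the subclasses as primary.
4. In the same edit, write the stop condition explicitly at H01 to H04 in SAP 9.2, and give anti-AChR-IgG one status across 8.3 and 9.1.

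The cost is a few sentences in the SAP, with no new data or analysis. The small downside is that subclass and by-visit differences can no longer be called statistically significant.

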13. IMMUNOGENICITY ANALYSIS

Immunogenicity analysis will be based on the safety population and the presence of anti-drug antibodies (ADAs) will be determined using the 3-tiered approach: screening, confirmation, and titration. All samples will be brought through the tier 1 screening assay to determine the potential presence of anti RVT-1401 antibody. All samples determined potentially positive will be analyzed in the tier 2 confirmation assay where presence of anti-RVT-1401 will be confirmed – the therapeutic antibody will be used to compete with the analytical responses of ADA to assess specificity of screened positive samples. After ADA confirmation, all samples that were confirmed positive for ADA will be analyzed in the tier 3 assay in order to characterize and determine antibody titers. Titration results will characterize the magnitude of the ADA response during the confirmatory assay.

Interpretation of the result will first be performed with a descriptive count of the immunogenicity assessment with a summary of ADA titer confirmed positive and a summary of immunogenicity rate by anti-RVT-1401 from confirmatory assay across all doses. Comparison will be performed between active and placebo treatment descriptively.

Optional analysis on ADA incidence and PK parameter descriptive presentation in ADA negative and positive confirmed subjects might be performed.

14. CHANGES FROM ANALYSES AS DESCRIBED IN THE PROTOCOL

- The definition of PP population was not included in the protocol but was defined as follows:

The PP analysis population includes all subjects who were randomized and received at least one 1 dose of study medication and had no major protocol deviations. Subjects will be summarized by randomized treatment for analyses based on the PP population.

- Below definition of 12-Week Follow-up Population was defined in the protocol but was not included the SAP.

The 12-Week Follow-up Population will include all participants who receive at least one dose of study treatment and decline participation in the OLE but continue with the 12-week follow-up period (ie, the non-OLE participants).

- The analysis populations defined in the SAP are not consistent with the protocol Section 10.2.1; the definitions in SAP were updated to comply with ICH E9.

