### **Expected Treatment Effect**

[figure not shown]
The proposed dosing regimens are expected to provide a sustained total IgG reduction of approximately 75-80% and 65-70% for Regimen A and B respectively, following the fourth or fifth dose. It is expected that the nadir IgG reduction will occur by the 5th dose and be maintained following the sixth dose before rising back to baseline over the next 6 to 8 weeks. These assumptions are supported by preliminary PD results, shown in Figure 1, from the ongoing Phase 1 clinical study RVT-1401-1001 (Section 3.2.3). In healthy participants, 4 weekly SC injections of 680 mg of RVT-1401 produced an average total IgG percent reduction from baseline of 78%.

For participants that enter into the OLE, IgG levels will rise over the 2-week interval between week 6 and the start of OLE dosing at week 8. The IgG levels are expected to oscillate between decreasing and increasing over the next 3 doses, with trough IgG levels expected to rise by 15-25% above the nadir levels achieved during the treatment phase in the double-blind part of the study. Subjects who switch to 340 mg every 2 weeks from the placebo treatment are expected to achieve an IgG reduction of approximately 35-45% after the last OLE dose. Upon completion of OLE dosing, all subject IgG levels are expected to return to baseline over the next 6-8 weeks.

In study RVT-1401-1001, the inter-individual variability in IgG reduction and PK was larger in the 340 mg cohort vs. the 680 mg cohort; this difference can be explained by lower receptor occupancy in the 340 mg cohort throughout the dosing interval across all individuals. It is also noteworthy that, with both doses, the variability in exposure decreased with repeat dosing. This may indicate that full receptor occupancy is not lost within the dosing interval, and that with subsequent doses, more receptors are being occupied or remain occupied.

In the repeat dose 340 mg cohort, there were some individuals who did not achieve nadir IgG concentration until after the last dose, indicating they may have not reached steady state. In contrast, most subjects in the 680 mg cohort achieved nadir concentration prior to the last dose and maintained that response until after the last dose, indicating steady state response was achieved. Data from this study will be used to support dose selection in future studies.

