## **12-Week Follow up Population**

The 12-Week Follow up Population will include all participants who receive at least one dose of study treatment in Part 1 and decline participation in the OLE but continue with the 12-week follow up period.

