### **10.3.6. Other Analyses**

#### **10.3.1. OLE and Follow up Analyses**

Data listings and summaries will be provided separately for the OLE and 12-Week Follow up Populations. Descriptive Analyses will be presented by randomized treatment assignment from the double-blind treatment period and overall. Baseline will be specified in the Statistical Analysis Plan. If there are multiple assessments collected on the same scheduled time, the average of these assessments will be used. Only the scheduled assessments will be included in the summary tables. All OLE and follow up analyses will be based on the OLE and 12-Week Follow up Populations, respectively. Ad hoc statistical analyses such as two sample t-test or Chi-Square test, may be performed for the changes or shifts at weeks 8, 10, and 12 separately. The significance will be evaluated at a 0.05 two-sided level for informational purposes only.

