5. GENERAL CONSIDERATIONS FOR DATA ANALYSES

Data will be listed and summarized. Listings will be sorted by treatment, participant, day, and time and include both scheduled and unscheduled visits; table summaries will be presented by treatment include placebo, RVT-1401 340 mg, RVT-1401 680 mg, combined RVT-1401 group, and by scheduled visit.

Open label extension period will start from the date of the first OLE dose for each subject. Unless otherwise specified, data collected during OLE period will be included in the same listings, tables, and figures with data collected during double-blind period.

Unless stated otherwise, descriptive summaries for continuous variables will include n, mean, standard deviation (SD), median, first and third quartiles (Q1, Q3), minimum, and maximum. The geometric mean with associated 95% confidence interval (CI) and the between-participant coefficient of variation (CV) (%CVb) for PK parameters only will also be included. For categorical variables, n and percent will be used as summary statistics. Baseline is the last available assessment prior to time of the first dose unless it is specified otherwise. If there are multiple assessments collected on the same scheduled time, the average of these assessments will be used. For tabulated safety summaries, only the scheduled assessments will be included in the summary tables.

In general, summary statistics for raw variables will be displayed as follows: minima and maxima will be displayed to the same number of decimal places as the raw data. Means, medians, and quartiles will be presented to 1 more decimal place than the raw data ; standard deviations will be presented to 2 more decimal places than the raw data.

The numbers of decimal places for summary statistics of derived variables (i.e., variables that are not measured by the study site but are calculated for analysis based on other measured variables) will be determined on a case by case basis.

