A summary of the number and percent of subjects in each analysis set will be provided by treatment group and in total. Analysis based on a 12-week Follow-up analysis set may be provided depending on the number of subjects who choose not to enroll in the OLE study phase.

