5.3. Subject Groups

For analyses based on the SAF analysis set or the PK analysis set, subjects will be grouped for analyses according to the actual treatment received. For all other analyses, subjects will be grouped for analyses according to randomized treatment assignment from the double-blind treatment period.

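### After Week 8 the SAP's default by-arm PD, laboratory and responder summaries mix re-dosed and off-drug participants, because the protocol's separate 12-Week Follow-up summaries have become optional with no trigger

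*SAP*

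**What the plan says.** **Protocol.** The section headed OLE and Follow up Analyses (the second one numbered 10.3.1) states: "Data listings and summaries will be provided separately for the OLE and 12-Week Follow up Populations". It bases all follow-up analyses on the second of these populations. Section 10.2.1 defines that population as participants dosed in the double-blind phase who "decline participation in the OLE but continue with the 12-week follow up period".

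**SAP on the follow-up set.** Section 14 lists among its changes: "Below definition of 12-Week Follow-up Population was defined in the protocol but was not included the SAP". It gives no reason specific to this set; a general bullet says that the populations were revised to comply with ICH E9. Section 5.1 is softer: "Analysis based on a 12-week Follow-up analysis set may be provided depending on the number of subjects who choose not to enroll" in the OLE. It states no number that would trigger the analysis.

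**SAP on pooling and grouping.** Section 5 says that, unless otherwise specified, "data collected during OLE period will be included in the same listings, tables, and figures with data collected during double-blind period". Section 5.3 groups safety and PK analyses by actual treatment, and then: "For all other analyses, subjects will be grouped for analyses according to randomized treatment assignment from the double-blind treatment period". Section 12 plans PD summaries, ANCOVA and line plots at all scheduled visits: "Analyses of PD endpoints will be provided for the PD analysis population". Section 10.2 summarizes laboratory values, with IgG and albumin among the parameters, at all scheduled visits. Section 9.4.2 summarizes responders at all timepoints. None of these three sections mentions OLE status.

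**The concern.** Once OLE dosing starts at Week 8, each double-blind arm can contain two kinds of participant: those re-dosed with 340 mg every two weeks, and those receiving nothing. The protocol planned to report them apart. Under the SAP's defaults a single row, such as total IgG for 680 mg at Week 12, covers both.

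Two questions are at stake. The first is the return of IgG after weekly dosing stops. Protocol 3.3.1 names sustained hypogammaglobulinemia as a risk, and Protocol 10.2.2 describes the second analysis as summarizing endpoints after the treatment-free phase. Non-OLE participants are the only ones who can be followed for 12 weeks after six weekly doses. The second is the OLE objective itself, the effect of switching to dosing every two weeks. A mean over both groups answers neither question.

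**Working it through.** The documents give no figure for OLE uptake or for a pooled post-Week 8 mean, so there is no stated figure to reproduce. The check traces the rules and then illustrates the size.

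**1. Do the rules lead to mixing?** SAP 5 pools unless another section says otherwise.

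| Output | Separated by period or OLE status? |
|---|---|
| Adverse events (10.1.6), PK (11), exposure (6.2), disposition (6.1), concomitant medication (10.4) | Yes |
| Change-in-score endpoints (9.4.1) | Defined through Week 7, before OLE dosing |
| PD (12) | No split; whole PD set, all scheduled visits |
| Laboratory values (10.2) | No split; all scheduled visits |
| Responders (9.4.2) | No split; all timepoints |

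PD and responder outputs follow the randomized arm (SAP 5.3). Laboratory outputs follow treatment received, which SAP 5.1 determines from the double-blind period if the dose level varied. Neither grouping separates re-dosed from off-drug participants.

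**2. Which visits?** Blood samples and MG assessments on dosing days are taken pre-dose, so Weeks 7 and 8 are unmixed. OLE doses fall at Weeks 8, 10 and 12. At Week 12, pre-dose, a non-OLE participant is 42 days past the last dose (Week 6) and an OLE participant 14 days past (Week 10). At Week 18 the intervals are 84 days (12 weeks after Week 6) and 42 days (6 weeks after Week 12). Total IgG is scheduled at every visit through Week 18. The chemistry panel, which includes albumin, has fewer visits, so the laboratory problem applies at whichever of them fall after Week 8.

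**3. Illustration: 680 mg, total IgG, Week 12.**

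Inputs from Protocol 3.2.2, Expected Treatment Effect:
- nadir reduction N = 75 to 80%;
- the reduction is held after the sixth dose "before rising back to baseline over the next 6 to 8 weeks", so r = 6 to 8 weeks;
- OLE troughs d = 15 to 25% above nadir.

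The arm size of 7 follows from 14 active and 7 placebo at 1:1:1.

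Assumptions: recovery is linear from the Week 6 dose, d is in points of baseline, and k = 4 to 6 of 7 enter the OLE.

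- Off drug: -N × (1 - 6/r). With r = 6 this is 0; with N = 80 and r = 8 it is -80 × 0.25 = -20%.
- OLE: -(N - d). From -(75 - 25) = -50% to -(80 - 15) = -65%.
- Pooled: [k × OLE + (7 - k) × off drug] / 7.
  - k = 4, N = 75, d = 25, r = 6: (4 × -50 + 3 × 0)/7 = -28.6%.
  - k = 6, N = 80, d = 15, r = 8: (6 × -65 + 1 × -20)/7 = -58.6%.

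**4. Sensitivity.**

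- d read as relative to the remaining IgG: OLE is -(100 - 25 × 1.25) = -68.8% to -(100 - 20 × 1.15) = -77%. Pooled is 4 × -68.75/7 = -39.3% to (6 × -77 - 20)/7 = -68.9%.
- Recovery clock started at Week 7: off drug is -75 × (1 - 5/6) = -12.5% to -80 × (1 - 5/8) = -30%. Pooled (d in points) is (4 × -50 + 3 × -12.5)/7 = -33.9% to (6 × -65 - 30)/7 = -60%.
- Only 1 of 7 in the OLE: as small as (1 × -50 + 6 × 0)/7 = -7.1%. With 0 or 7 of 7 there is no mixing.
- Placebo arm, 4 of 7 in the OLE, using the protocol's 35 to 45% reduction after the last OLE dose and no change off drug: 4 × -35/7 = -20% to 4 × -45/7 = -25.7%.

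**The case against.** The strongest case for the plan has five parts.

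- **The change is disclosed, and the analysis is not abolished.** A reader of SAP 14 might infer that the follow-up analysis is gone. SAP 5.1 does not support that, since it keeps the analysis as an option. What stands against the plan is that the two sections disagree, the option has no trigger, and SAP 14 does not say that the protocol's promise of separate summaries was relaxed.
- **Pooling is a default with exceptions.** Several outputs are separated, and the SAP keeps an OLE analysis set with its own baseline. Sharing a table also need not mean sharing a cell. This narrows the point to PD, laboratory and responder outputs. For those, the SAP names no OLE-status column, and SAP 12 names only the PD population.
- **Recovery can still be seen.** A reader might infer that the trial cannot show recovery. That goes too far: Weeks 7 and 8 are unmixed, listings keep individual data, and the optional analysis may be run. The limitation is in the default by-arm summaries after Week 8.
- **The figures rest on assumptions.** This is correct. Uptake, linearity and the meaning of 15 to 25% are not given. Nor is it safe to say that a pooled mean would be taken as failure to recover, or that off-drug participants would be at baseline by Week 12. Protocol 3.2.3.3 reports only that IgG was within 30% of baseline five weeks after four weekly doses. Even at -30% off drug, the smallest OLE value above (-50%) is 20 points away.
- **Safety oversight does not depend on these tables, and recovery is not a listed endpoint.** Both are true: an unblinded Medical Monitor reviews IgG on an ongoing basis. The protocol's reporting commitment remains, and the OLE objective, which is listed, is blurred by the same pooling.

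**Conclusion.** The point holds in a limited form. The protocol requires separate OLE and follow-up summaries. The SAP makes the follow-up set optional without a trigger and, by default, mixes re-dosed and off-drug participants in the PD, laboratory and responder summaries after Week 8. This happens in any arm where 1 to 6 of 7 enter the OLE.

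The range of -29% to -59% for 680 mg at Week 12 is an illustration under the stated assumptions, not a forecast. Other readings move the values but leave the mixing in place.

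The Week 7 primary analysis, Weeks 7 and 8, adverse events, PK, exposure, disposition and concomitant medication are not affected. The documents do not support saying that the follow-up analysis has been removed outright or that recovery cannot be shown at all. This should be corrected before the final tables are produced, but it does not threaten the primary result.

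**What to change.** 1. Restore the 12-Week Follow-up set in SAP 5.1 as a required analysis set, using the protocol's definition, and align SAP 14 with it.
2. In SAP 12, 10.2 and 9.4.2, state that tables and figures after Week 8 are shown separately by OLE status within each double-blind arm (as randomized, or as treated for laboratory values).
3. Where non-OLE numbers are very small, show individual profiles instead of a mean.
4. Base statements on recovery on non-OLE participants through Week 18, and on OLE participants by time since last dose.

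The cost is SAP wording and extra columns, with no new data. The downside is small cells, since an arm of about 7 is split in two.
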